6.4.1 Categories of prior and concomitant medications

Medications will be classified as follow based on imputed start and stop dates & times as outlined in [Section 4.2.2](#).

- **Past** medications will include any medications that started and stopped before the first administration of IMP.
- **Prior** medications will include any medications that started before the first administration of IMP.
- **Baseline** medications will include any medications that started prior to dosing and continued after (classified as prior and concomitant medications).
- **Concomitant** medications will include any medications that have been taken at least once after the first administration of IMP during the Treatment and/or Observation Period.
- **Concomitant Only** medications will include any medication that started after the first administration of IMP and continues during the Treatment and/or Observation Period.

Table 6–1: Concomitant Medications Classification

Medication Started	Medication finished	Classification
Before 1 st Dose IMP	Before 1 st Dose IMP	Past
Before 1 st Dose IMP	Any time	Prior
Before 1 st Dose IMP	After 1 st Dose IMP	Baseline (= prior and concomitant)
Any time	After 1 st Dose IMP	Concomitant
After 1 st Dose IMP	After 1 st Dose IMP	Concomitant Only

6.4.2 Assignment of medications to study period

The following rules will be used to assign a concomitant medication to a study period:

- **Treatment Period:** a medication will be assigned to the Treatment Period if it has been taken at least once between the first administration of IMP on Day 1, up to the minimum of Day 43 and 7 days after the last dose of IMP. This includes medications that started prior to the Treatment Period and those that continued into the Observation Period.
- **Observation Period:** a medication will be assigned to the Observation Period if it has been taken at least once from the day after Treatment Period to the EOS visit. This includes medications that started prior to the Observation Period.

Thus, a medication taken from the time of the first drug administration in the Treatment Period to the end of the study will be assigned to the Treatment Period and the Observation Period.

6.4.3 Baseline MG medication definition

MG Baseline medication is defined as an indication related to MG and includes one of the following ATC codes:

- [REDACTED] (Corticosteroids)
- [REDACTED] (Immunosuppressants)
- [REDACTED] (Parasympathomimetics)

7 MEASUREMENTS OF TREATMENT COMPLIANCE

Not applicable. The number of infusions will be recorded as detailed in [Section 10.1](#).

8 EFFICACY ANALYSES

All efficacy analyses will be performed using the RS unless specified otherwise, including for the interim analysis.

8.1 Handling of intercurrent events

The main intercurrent events (ICEs) of interest are:

- ICE1 – The use of rescue therapy prior to Day 43 (Visit 10)
- ICE2 – Permanent treatment discontinuation (or withdrawal from study) due to TEAEs

Two additional types of ICEs will be included to account for data affected by the COVID-19 pandemic as follows:

- ICE3 – Treatment discontinuation due to suspected/confirmed COVID-19 infection (“Confirmed COVID-19” or “Suspected COVID-19” as the relationship to COVID-19 in the COVID-19 Impact eCRF)
- ICE4 – Treatment discontinuation due to non-COVID-19 infection related issues (“General circumstances around COVID-19 pandemic without infection” or “other” as the relationship to COVID-19 in the COVID-19 Impact eCRF)

The number and percentage of study participants with each intercurrent event will be summarized by treatment group and RLZ total.

The strategies to handle ICEs are summarized as below:

Strategies	Description
Hypothetical & treatment policy strategy	
If study participants experience ICE1, data at and after the point of the ICE for the purpose of analysis will be treated as missing and imputed under proposed method per Section 4.2.1.
 
For participants experiencing ICE2-4, data in the Treatment Period from Baseline to Day 43 will be used regardless of whether any ICEs occurred, missing data will be imputed per Section 4.2.1.
 
For participants who permanently discontinue treatment or withdraw from the study during Treatment Period and who continue into the Observation Period, the observation phase data (collected bi-weekly) will be mapped to the nearest visit for primary analysis where treatment windows will be utilized for the mapping.

Treatment policy strategy	The data in the Treatment Period from Baseline to Day 43 will be used regardless of whether any intercurrent events occurred.
Composite strategy	The occurrence of any intercurrent events above will be handled by evaluating the corresponding study participants as treatment failures and imputed with a worst score (continuous) or non-responder (binary).
COVID-19 Hypothetical strategy	
If participant experience ICE1 and/or ICE2, then data at and after the point of the intercurrent event for the purpose of analysis will be treated as missing.
 
Additionally, participant experience ICE3, ICE4 or those that have visits in treatment period affected (e.g. visit performed by video call) will be completely removed from analysis.

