3.2 General study level definitions

3.2.1 Analysis time points

All data will be analyzed based on the visits identified per the Schedule of Activities in protocol. Mapping to analysis visit windows is not applied, except for premature end of treatment (PEOT) visits (specified in [Section 3.2.3](#)).

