3.2.2 Study periods

The maximum duration of the study per participant will be approximately 18 weeks, consisting of the following 3 periods:

- Screening Period: 1 to 28 days
- Treatment Period: 6 weeks
- Observation Period: 8 weeks

The end of the study is defined as the date of the last visit of the last participant in the study.

The following definitions for starting and entering the study periods will be applied:

- **Treatment Period** starts with the first day of IMP and ends after Day 43/PEOT assessments. All participants in the Safety Set will be considered to have started the Treatment Period. A participant is considered to have completed the Treatment Period if assessments from Treatment Period Day 43 are completed.
- **Observation Period** starts one day after the end of the Treatment Period and ends after the final assessments on the last visit. Participants with assessment on any Observation Period day are considered to have started the Observation Period. Participants who have a completed status in the study termination case report form are considered to have completed the Treatment and Observation Periods.

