8.2.4.2 Supplementary Analysis #2

The second supplementary analysis of the primary endpoint will be performed using a treatment policy strategy (see details in [Section 8.1](#)) based on the RS. Any missing MG-ADL scores will be handled based on maximum likelihood estimation method under MAR assumption.

The same stage-wise analysis approach as primary analysis ([Section 8.2.2](#)) will be repeated.

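### Supplementary Analysis #2, the treatment-policy analysis, has no rule for using MG-ADL scores taken after a participant moves early into the Observation Period, although the primary analysis uses them

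*SAP*

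**What the plan says.** SAP 8.2.4.2: "The second supplementary analysis of the primary endpoint will be performed using a treatment policy strategy", on the Randomized Set, with missing scores handled by maximum likelihood under MAR. It refers to 8.1 for the strategy and to 8.2.2 for the stage-wise model.

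SAP 8.1, treatment policy row, in full: "The data in the Treatment Period from Baseline to Day 43 will be used regardless of whether any intercurrent events occurred".

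SAP 8.1, hypothetical & treatment policy row (the primary strategy): data from the point of rescue onward are set to missing. For the other three intercurrent events, Treatment Period data to Day 43 are used. A separate sentence follows. "For participants who permanently discontinue treatment or withdraw from the study during Treatment Period and who continue into the Observation Period", it says, "the observation phase data (collected bi-weekly) will be mapped to the nearest visit for primary analysis", using treatment windows.

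SAP 3.2.2: the Treatment Period "starts with the first day of IMP and ends after Day 43/PEOT assessments", and the Observation Period "starts one day after the end of the Treatment Period and ends after the final assessments on the last visit".

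SAP 3.2.1: "Mapping to analysis visit windows is not applied, except for premature end of treatment (PEOT) visits". Section 3.2.3 then assigns the PEOT assessment itself to the next scheduled site visit, and says nothing about later scores.

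Protocol 7.1.3 and 7.2 send participants who permanently stop for the listed events, or who withdraw during treatment, into the Observation Period. MG-ADL is scheduled at all four of its visits (Protocol 1.3).

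**The concern.** Under SAP 8.1 both strategies take a treatment-policy approach to TEAE and COVID-19 discontinuation. The difference one would expect between them is rescue: the primary discards post-rescue data and Supplementary Analysis #2 keeps them. SAP 8.2 gives the purpose of this analysis as bringing intercurrent events into the treatment paradigm.

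As written there is a second difference, and it runs the wrong way. A participant who stops IMP for a TEAE, has a PEOT visit and enters the Observation Period before Day 43 contributes off-drug scores to the primary but not to Supplementary Analysis #2. The mixed model then fills in Day 43 from participants in the same arm, most of them still on drug. A gap between the two results could not be put down to rescue alone, and the analysis named for the effect regardless of intercurrent events would not fully deliver it.

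**Working it through.** The plan states no figure for this, so the check is first textual and then illustrative.

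**Which data enter.**
1. The treatment policy row admits Treatment Period data only (8.1).
2. That period ends at PEOT for an early discontinuer (3.2.2), so scores after PEOT are Observation Period data.
3. The only rule that brings them back is in the other row of 8.1 and is worded for the primary analysis.
4. Section 3.2.1 sets the default of no window mapping except for PEOT visits. Section 8.2.2, the model section that Supplementary Analysis #2 repeats, has no mapping rule.
5. Within 8.1, the primary row uses the same Treatment Period wording for the non-rescue events and still adds the mapping sentence. The SAP therefore does not treat that wording as already covering Observation Period scores.

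**Which visits are lost.** The Schedule places Observation visits at Days 57, 71, 85 and 99, which are 14, 28, 42 and 56 days after Day 43. Assumption: for an early discontinuer they fall at the same intervals after PEOT. The mapping sentence presupposes something like this, because visits fixed at Days 57-99 would fall in no treatment window. With windows of ±2 days and model visits at Days 8, 15, 22, 29, 36 and 43 (8.2.2):

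| PEOT on Day | Post-PEOT scores that would map to |
|---|---|
| 8 | Days 22 and 36 |
| 15 | Days 29 and 43 |
| 22 | Day 36 |
| 29 | Day 43 |
| 36 | none (next score on Day 50) |

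Two of the five PEOT days give a score at Day 43 itself. The primary uses these scores if no rescue was given; Supplementary Analysis #2 as written uses none of them.

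**Size.** Direct shift in an active arm's Day 43 mean = d × f × L, with:
- d, the share who permanently stop and enter the Observation Period without rescue: 4-8%, assumed;
- f, the share of PEOT days giving a Day 43 score: 2/5 = 0.4, taking the five days as equally likely;
- L, the points by which off-drug scores are worse than the MAR prediction: 1.5-2.0, assumed to equal loss of the whole treatment effect in SAP 2.4.

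Low: 0.04 × 0.4 × 1.5 = 0.024. High: 0.08 × 0.4 × 2.0 = 0.064. So about 0.02-0.06 points, or 0.024/1.5 = 1.6% to 0.064/2.0 = 3.2% of the assumed effect. Earlier mapped scores would add somewhat through the within-participant correlation; this is not counted.

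**The case against.** **The mapping sentence may be a general convention.** It is tied to no particular intercurrent event, Supplementary Analysis #2 repeats the primary's approach, and its purpose is plain. That may well be the intent. But the sentence names the primary analysis, and what is repeated is 8.2.2, which has no mapping rule. A programmer following the text and one following the presumed intent would build different datasets.

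**Section 3.2.1 cannot bar the mapping.** Read strictly it would bar the primary's mapping too, so 8.1 evidently overrides it. This stands: 3.2.1 only sets the default where no specific rule exists, and the treatment policy row has none.

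**The SAP follows the protocol.** Protocol Table 9-1 defines this analysis by treatment-period data to Day 43. True, but the same table also applies a hypothetical strategy to TEAE discontinuation in the primary. SAP 3.9 records that the strategies have since been updated, and the supplementary row carries no matching mapping rule.

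**A reader might infer that all scores after TEAE and COVID-19 discontinuation are lost.** The documents do not support that.
- Protocol 7.1.4 treats COVID-19 infection or exposure as a reason for temporary discontinuation with the visit schedule kept.
- Participants rescued during treatment complete their remaining visits (Protocol 4.1).
- Protocol 7.1.1 tells participants stopped on liver chemistry to follow the visit schedule, and those who keep the treatment visits are unaffected. Item 7 of 7.1.3, however, moves those meeting permanent liver criteria into the Observation Period; the two passages need reconciling.
- The PEOT score is kept in both analyses (SAP 3.2.3). If PEOT follows a completed Visit 9, it supplies Day 43.

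**Rescue narrows the contrast.** Protocol 9.3 expects TEAE discontinuers to be likely to start rescue, and the primary discards their post-rescue scores too. This shrinks the difference between the analyses, but a treatment-policy analysis should still use those scores.

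**Conclusion.** The gap is real but limited. It concerns participants who permanently stop IMP, have a PEOT visit and enter the Observation Period before Day 43, mainly after TEAEs. For them the treatment-policy analysis, read literally, uses less off-drug data than the primary whenever no rescue was given.

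Under the assumptions above the direct effect is about 0.02-0.06 MG-ADL points. The discontinuation rate, the even spread of PEOT days, the 14-day spacing from PEOT and the off-drug loss are all assumptions. A reader might infer a larger bias by applying a 2-3 point deficit to all of an 8% discontinuation rate (0.08 × 2 = 0.16 to 0.08 × 3 = 0.24). The documents do not support that: only some PEOT days give an unused Day 43 score, and such a deficit equals or exceeds the whole assumed effect of 1.5-2.0 points.

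The primary result and alpha control are untouched, because Supplementary Analysis #2 is outside the testing procedure in SAP 4.6. It is still worth correcting, because as written the analysis does not fully estimate what its name says.

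**What to change.** 1. In SAP 8.1, state that the mapping of observation-phase scores (up to Day 43, nearest visit, same windows) also applies to the treatment policy strategy of Supplementary Analysis #2, there including scores after any later rescue.
2. Delete the words that restrict the mapping to the primary analysis. This also removes doubt about the sensitivity, exploratory and secondary analyses run under the primary's strategy.
3. List this mapping in SAP 3.2.1 as a second exception beside PEOT visits.
4. Reconcile Sensitivity Analysis #4, which is hypothetical & treatment policy in SAP 8.2 and Table 8-2 but treatment policy in 8.2.3.4. The label decides whether post-rescue data are used and, until item 1 is done, whether the mapping applies.

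The cost is a few sentences of SAP wording. No new data are needed, and the derivation is already required for the primary analysis; the one addition is keeping post-rescue scores in Supplementary Analysis #2.

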Some study-specific investigations may not be conducted according to the study protocol during a pandemic or other exceptional circumstances (eg, hurricanes) due to the need to implement safety measures and guidance from regulatory authorities. In such a situation, which may be accompanied by local or global containment or other measures, sites may need to prohibit access to study participants and study-related personnel. Study participants visits to the study site may be replaced by contingency measures. These measures are primarily established to ensure the safety of study participants during the course of the study and to maintain the study participants treatment schedule, if the Investigator considers it appropriate. These measures include but are not limited to virtual visits or home-nursing visits replacing site visits, eg, telemedicine contacts

or home-nursing visits when treatment and/or blood sampling is scheduled. The contingency measures are described in a contingency plan and will be implemented as required.

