8.1.4.1 MG-Activities of Daily Living

Independently of study visit type (site, home, or virtual), the MG-ADL must be completed by study participants in a quiet place by themselves without the help of a partner or caregiver, before any clinical examination takes place. Study participants should be informed of the importance of this questionnaire and instructed to read the items and instructions carefully. They should be informed that there are no correct or incorrect answers.

Study personnel are not allowed to interpret the items for the participant. If a participant asks for guidance, study personnel should instruct him/her to respond according to their best understanding of the item. The MG-ADL should only be checked for completeness by study personnel. In the event a few questionnaire items have not been completed, study personnel should only query this with the study participant, if this results from an omission. Study personnel shall neither complete missing data nor suggest changes to participant responses. As with other study data, responses to the questionnaire should be treated as confidential information. Data privacy considerations apply.

In the specific context of virtual and home visits, paper copies of the MG-ADL should be made available to study participants ahead of the visit. Site coordinators or study personnel (or an automatic alert mechanism) should remind study participants to complete the MG-ADL before visit start and to record the date upon completion of the questionnaire. Once they have completed the MG-ADL, study participants should transfer it electronically to site personnel. In the event study personnel finds out that the MG-ADL has not been completed before the visit, study participants should be allowed some additional time to complete the questionnaire before any study related assessment is initiated.

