3.5.2 Randomized Set

The Randomized Set (RS) will consist of all study participants who were randomized, using the treatment assigned instead of the actual treatment received.

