8.2 Statistical analysis of the primary efficacy endpoint

The primary efficacy endpoint is the change from Baseline in MG-ADL score to Day 43 (Visit 10) and will be evaluated under the ‘hypothetical & treatment policy’ estimand based on RS using Hypothetical & Treatment Policy strategy.

Missing data in the primary analysis will be handled under a missing at random (MAR) assumption.

To check the assumptions around the estimand in the (primary) analysis of the primary endpoint, the following sensitivity and supplemental analyses will be performed:

- A sensitivity analysis using:
 - Hypothetical & treatment policy strategy on FAS;
 - Hypothetical & treatment policy strategy with a J2R approach on missing data will be used to verify the robustness of the MAR approach;
 - Hypothetical & treatment policy strategy based on the subgroup of the RS who received all [REDACTED] doses.
 - Hypothetical & treatment policy strategy based on the subgroup of the FAS excluding confirmed COVID-19 cases.
- A supplemental analysis using:
 - Composite strategy to handle the occurrence of an intercurrent event as treatment failures. A trimmed mean approach will be implemented to impute missing data;
 - Treatment policy strategy to allow intercurrent events to be included in the treatment paradigm.

An additional analysis will be performed using COVID-19 Hypothetical strategy on RS.

The methods to handle the missing data caused by occurrence of ICEs in each analysis are detailed in [Section 4.2.1](#).

Please see below for details about the estimands attributes for the evaluation of the primary endpoint (primary, sensitivity and supplemental analyses).

1. Treatment Conditions: please see table below.

Table 8-1: Treatment Conditions:

Study Treatment Name:	Rozanolixizumab (Treatment Arm 1)	Rozanolixizumab (Treatment Arm 2)	Placebo (Treatment Arm 3)
Dosage formulation:	Solution for infusion	Solution for infusion	Aqueous solution
Unit dose strength(s)/Dosage level(s):	[REDACTED]		0.9% sodium chloride aqueous solution (physiological saline, preservative free)
Route of Administration	Subcutaneous (sc)		

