8.2.5 Additional Analysis

An additional analysis of primary endpoint will be performed on RS under the COVID-19 hypothetical strategy (see details in [Section 8.1](#)). The same stage-wise analysis approach as primary analysis ([Section 8.2.2](#)) will be repeated.

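### The additional COVID-19 analysis is called a hypothetical strategy on the Randomized Set, but it removes whole participants after randomisation, even for a video visit at which MG-ADL is still valid

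*SAP*

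**What the plan says.** SAP 8.1 describes the COVID-19 hypothetical strategy in two parts. After rescue therapy (ICE1) or discontinuation due to TEAEs (ICE2), scores from that point on are treated as missing. For COVID-19-related discontinuation (ICE3, ICE4) the participant is dropped altogether, and the same applies to others: "those that have visits in treatment period affected (e.g. visit performed by video call) will be completely removed from analysis". Beyond the video-call example, the SAP does not define an affected visit.

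SAP 8.2 states: "An additional analysis will be performed using COVID-19 Hypothetical strategy on RS". SAP 8.2.5 repeats this and applies the stage-wise primary model. SAP 8.3.2 to 8.3.6 use the same approach for MG-C, QMG and the three MG Symptoms PRO scores. SAP 3.5.2 says that the RS "will consist of all study participants who were randomized, using the treatment assigned instead of the actual treatment received".

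Protocol 8.1.4.1 gives one instruction for every mode of visit: "Independently of study visit type (site, home, or virtual), the MG-ADL must be completed by study participants in a quiet place by themselves". It also explains how the form is supplied before, and returned after, home and virtual visits. Protocol Section 8 lists "virtual visits or home-nursing visits replacing site visits" among the contingency measures.

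**The concern.** A hypothetical strategy asks what the score would have been had the event not happened. It makes the affected scores missing and keeps the participant and the earlier data. Removing the participant changes the population instead, and the set analysed is then no longer the RS.

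The purpose of this analysis is to show whether the primary result is robust to the pandemic. As written, a difference from the primary result could come from COVID-19 itself, from a changed population or from lost precision, and a reader could not tell which. Agreement would also reassure less than the label suggests, because it would describe only participants with an undisturbed treatment period.

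**Working it through.** **1. The passages side by side.**
- *Rule against analysis set.* SAP 8.1 removes participants; SAP 8.2 and 8.2.5 say RS; SAP 3.5.2 makes the RS everyone randomised. These cannot all hold.
- *Rule against label.* SAP 8.4.4 applies the same exclusions descriptively and openly calls the result COVID-19 free participants. SAP 8.2 labels its other restricted analyses, such as those who received all doses, as subgroups. This analysis alone keeps an estimand name and the RS.
- *Video visits.* Protocol 1.3 schedules MG-ADL at Visits 11 and 13, which are virtual by default. SAP 8.1 maps Observation Period data into the primary analysis for early discontinuers. The plan therefore accepts virtual MG-ADL in one place and removes a participant for a video visit in another.
- *Other instruments.* The MG Symptoms PRO is self-completed, and Protocol 7.1.4 allows PROs to continue virtually. It is not scheduled at Day 22 or Day 36 (Protocol 1.3), yet an affected visit on either day removes the participant from its analysis too. QMG includes forced vital capacity and limb strength, and most MG-C items need examination (Protocol 8.1.2, 8.1.3), so a video visit can genuinely make those scores unobtainable.

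**2. The plan's own figures.** The SAP gives no figure for this analysis. Its power figures (Table 2-1) use everyone randomised. A simulation of the design in SAP 2.4 and 4.4.1, with 100,000 runs for each of eight scenarios, reproduces power within 0.5 percentage points and average sample size within 1%. Scenario 7, for example, gives 0.946 against 0.943, and 190.6 against 189.9 participants.

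**3. Share removed.** SAP 8.2.2 puts six post-Baseline visits in the MMRM (Days 8, 15, 22, 29, 36, 43). Let q be the chance that a visit is affected, assumed equal and independent across visits. Then

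share removed = 1 − (1 − q)^6

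and, if only affected scores were set to missing, the share of Day 43 scores lost is about q, before counting scores after missed doses. The approximate factor on the standard error, with equal removal across arms, is 1/√(1 − share removed). Total N of 150 to 240 is from SAP 2.4.

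| q (assumed) | Participants removed | Number, N = 150 to 240 | SE factor | Day 43 scores lost, visit-level rule |
|---|---|---|---|---|
| 1% | 1 − 0.99^6 = 5.9% | 9 to 14 | 1.03 | about 1% |
| 2% | 1 − 0.98^6 = 11.4% | 17 to 27 | 1.06 | about 2% |
| 5% | 1 − 0.95^6 = 26.5% | 40 to 64 | 1.17 | about 5% |

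The model is fitted by stage. At 26.5% removed, a Stage 1 arm of 30 falls to 30 × 0.735 ≈ 22.

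**4. Bias.** Suppose removed participants score g points worse than retained ones in every arm, and fractions f_A (active) and f_P (placebo) are removed. The retained treatment difference shifts by −(f_A − f_P) × g. Equal removal gives no shift. An invented imbalance of 30% against 10% with g = 1 to 2 gives −0.2 to −0.4 points, in favour of active.

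**The case against.** The strongest reply is that little depends on this analysis. SAP 8.2 calls it additional, it has no row in Table 8-2, and it plays no part in the testing procedure of SAP 4.6. The primary analysis keeps every RS participant and uses observed data after ICE2 to ICE4; Supplementary Analysis #2 also keeps observed data. A reader might infer that the trial's randomised comparison is compromised. The documents do not support that: the exclusion is confined to this check and its repeats. This part of the reply stands.

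A second reply is that a video visit can matter. Five of the six MMRM visits (Days 8 to 36) are dosing visits, and a video call cannot deliver an infusion. Protocol 7.1.4 lets virtual PROs continue while dosing is held and permits no make-up dose. A video visit may therefore mark a missed dose, and scores after it are not scores free of the event. This also stands, and the fix has to allow for it. It does not justify deleting scores from before the missed dose.

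Third, the intent is visible: SAP 8.4.4 already names the subset. That is true, but SAP 8.1, 8.2 and 8.2.5 do not carry the name.

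Finally, the size rests on assumed rates. That is so, and it is why only a range is given.

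**Conclusion.** The point holds for the additional, non-confirmatory COVID-19 analysis of the primary endpoint and its repeats for the five continuous secondary endpoints. The rule is a post-randomisation exclusion, and neither its name nor its stated analysis set describes it. On an assumed independent per-visit rate of 1% to 5%, it removes about 6% to 27% of participants, against about 1% to 5% of Day 43 scores under visit-level handling. The second figure does not count scores after missed doses. The true rate is not in the documents, and affected visits that cluster within participants would lower the share removed.

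Two further readings should not be drawn. One is that the analysis is biased towards active treatment. Removal for logistic reasons is probably unrelated to arm under blinding. Removal for infection (ICE3) could differ by arm, since serious infection is a listed potential risk (Protocol 2.3), but nothing in the documents shows an imbalance. The other is that video visits are harmless for every endpoint. That argument covers MG-ADL explicitly and the MG Symptoms PRO by its self-completed nature; it does not cover QMG or the examined MG-C items.

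**What to change.** In SAP 8.1, keep all RS participants in this analysis. Leave the handling of ICE1 and ICE2 as it is, and otherwise set to missing, under MAR in the same MMRM, only:
- scores after ICE3 or ICE4;
- scores after a dose missed because of COVID-19;
- scores at visits where that instrument could not be validly assessed, for example QMG or examined MG-C items by video.

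Keep self-completed MG-ADL and MG Symptoms PRO scores from virtual visits where no COVID-19-related dose had been missed beforehand. Since PROs precede dosing on dosing days (Protocol 8.1.4), a score at the visit where the first such dose is missed can stay.

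Define an affected visit from the COVID-19 Impact eCRF, which already records impacted visits and impact categories (SAP 4.2.3).

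If the complete-removal version is also wanted, present it as a subset of COVID-19 free participants, as in SAP 8.4.4, and drop both the RS and the hypothetical label.

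The cost is SAP wording and a little more data handling: a decision per visit and instrument in place of one exclusion flag per participant.
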